### **5.13.3 Clinical Laboratory Data**

Observed clinical laboratory data and change from baseline values will be summarized by time period for hematology, chemistry and numeric urinalysis using the periods specified in Section 5.4.2 Table 2. For each laboratory parameter collected for each subject, within each time period, 2 different representations will be used for generating

the population summary statistics: the highest and lowest measurement from that subject during that particular time period. The highest or lowest measurement will capture the worst or the most extreme observed value (depending on the laboratory test, the highest or lowest or both can be concerning). In addition to each time period, for each laboratory parameter, the last, highest and lowest measurement collected for each subject during the entire study period will also be summarized.

For a subset of clinical laboratory parameters (red blood cell count, hemoglobin, white blood cell count, neutrophils, alkaline phosphatase, alanine aminotransferase, aspartate aminotransferase, bilirubin (total), gamma-glutamyl transferase, creatine phosphokinase, lactate dehydrogenase, blood urea nitrogen, creatinine, and uric acid) low [L], normal [N] or high [H] status will be determined based on the normal ranges provided by the testing laboratory.

The count and percentage of subjects with markedly abnormal post-baseline clinical laboratory parameters tabulated for all subjects and a subset of subjects with normal baseline will also be presented by time period and overall as defined in [Table 2](#) and for overall study period. The criteria for markedly abnormal laboratory values are provided in [Appendix B](#). For each laboratory parameter, within each specified time period and for overall study period, if a subject has at least 1 measurement meeting the marked abnormal criterion, this subject will be counted as having an incidence. The denominator for each laboratory parameter within each specified time period will be the total number of subjects with baseline and at least 1 post-baseline value within that particular time period.

Clinical laboratory data will be displayed in data listings with date and study day of collection. All units will be displayed according to the Système International (SI) conventions for units. Out-of-range values will be flagged in the data listings (i.e., 'L' or 'H').

The routine laboratory panel includes:

#### Hematology

Complete blood count including White Blood Cell Count, Complete Differential (Relative and Absolute), Hematocrit, Hemoglobin, Red Blood Cell Count, Platelets, and Reticulocyte Count.

#### Clinical Chemistry

Sodium, Potassium, Chloride, Phosphorus, Calcium, Carbon dioxide, Blood urea nitrogen, Creatinine, Uric acid, Alanine Aminotransferase, Aspartate Aminotransferase, Gamma-Glutamyl Transferase, Alkaline Phosphatase, Total Bilirubin, Lactate Dehydrogenase, Albumin, Total Protein, and Creatine Kinase/Creatine Phosphokinase.

## Urinalysis

Blood, Red Blood Cells, White Blood Cells, Protein, Glucose, Ketones, Specific Gravity, and pH (only the pH and specific gravity information was presented in the summary table; all urinalysis data was presented in a listing)

### **5.13.4 Vital Signs and Weight**

#### **5.13.4.1 Vital Sign Parameters**

Vital signs are collected at every study visit. A summary of observed values and change from baseline by time period will be presented for orthostatic blood pressure (systolic and diastolic in mmHg) and pulse (beats per minute), measured supine (after 5 minute), and standing (after 1 minute), respiratory rate, oral temperature and weight. For each vital sign parameter collected for each subject, within each time period, 2 different representations will be used for generating the population summary statistics: the highest and lowest measurement. The highest or lowest measurement will capture the worst or the most extreme observed value. In addition to each time period, for each vital sign parameter, the last, highest and lowest measurement collected for each subject during the entire study period will also be summarized.

All observed and change from baseline vital sign values will be provided in a listing with date of collection, study day, and time period.

#### **5.13.4.2 Orthostatic Hypotension**

Orthostatic hypotension is assessed each time vital signs are collected for pulse and blood pressure through the comparison of 5 minute supine results against 1 minute standing. The count and percentage of subjects experienced orthostatic hypotension as defined below will be summarized for each time period defined in [Section 5.4.2 Table 2](#) and for overall study period (at any timepoint postdose) for subjects for whom orthostatic hypotension was not present at baseline. If a subject has at least 1 measurement meeting the orthostatic hypotension criteria during a given time period, this subject will be counted as having an incidence for that time period. The denominator for percentages is the number of subjects with non-missing data at each visit.

Orthostatic hypotension occurs if:

- there is a decrease of  $\geq 20$  mmHg in systolic blood pressure (SBP)  
OR
- there is a decrease of  $\geq 15$  mmHg in diastolic blood pressure (DBP)  
OR
- there is an increase of  $\geq 20$  bpm in pulse rate (PR);

each measured from 5 minutes supine to 1 minute standing at the same visit.

An overall count and percentage of subjects experienced orthostatic hypotension based on findings from either AE records (i.e. where the preferred term = 'Orthostatic

hypotension') or vital signs (orthostatic changes in blood pressure and pulse) will also be presented. Data listing of blood pressure and pulse measurements for these subjects will also be presented.

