Central nervous system and gastrointestinal disturbances were the most common AEs. Central nervous system events included headache, postural dizziness, somnolence (drowsiness), and dizziness. Gastrointestinal disturbances included nausea, constipation, dyspepsia, and vomiting; severe nausea and vomiting occurred and were dose-limiting in a few cases. Other reported, but less common, AEs included psychiatric conditions such as confusion and hallucinations. Cardiac-related and cardiovascular AEs were infrequent and included ventricular tachycardia, bradycardia, and vasovagal and syncopal episodes. Other infrequent AEs included orthostatic hypotension, asthenia, fatigue, peripheral edema, and injury especially due to a fall.

[REDACTED]

Although the number of SAEs in the Parkinson's disease patients who received pimavanserin may appear disproportionately high, this group reflects subjects who participated in the long-term open label safety extension studies where duration of dosing is markedly longer than in the other groups.

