6.2.5. Vital Signs

All vital sign measurements will be performed by appropriately qualified and authorized study personnel. Vital signs will be measured and recorded on the appropriate CRF pages on Day 1 (Baseline) for those subjects that enroll in this study greater than one week following completion of the previous blinded study. In addition, vital signs will be measured and recorded for all subjects at the Week 2 visit, Month 1 visit, Month 3 visit, Month 6 visit, Month 9 visit, Month 12 visit and every 6 month visit thereafter, and if a subject withdraws or is terminated from the study, at an End-of-Study visit.

Blood pressure (BP), including systolic BP (SBP) and diastolic BP (DBP), will be measured in the same arm at each visit by using a manual or automated sphygmomanometer. The results will be recorded in millimeters of mercury (mmHg) on the appropriate CRF pages. Pulse rate will be measured in the radial artery in the dominant arm for 30 seconds and will be recorded as beats per minute (bpm). Respiratory rate (RR) will be measured and recorded in breaths/minute. Oral temperature will be measured using a digital thermometer.

Each time vital signs are measured the following procedures for orthostatic BP and pulse rate evaluation should be followed:

After the subject is supine for approximately 5 minutes, BP and pulse rate will be measured and the subject will then be instructed to rise to a standing position. BP and pulse rate will be again measured 1 minute after standing.

Potentially clinically significant orthostatic findings include:

- SBP drop of 20 mmHg or more
- DBP drop of 15 mmHg or more
- Pulse rate increase of 20 bpm or more and/or
- Emergence of clinical symptoms (e.g., dizziness) after standing.

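### The combined orthostatic count in SAP 5.13.4.2 misses subjects whose only orthostatic finding is symptomatic, because it omits the protocol's symptom criterion and searches AEs for one preferred term

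*SAP*

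**What the plan says.** Protocol 6.2.5 describes a supine reading followed by a standing one: "BP and pulse rate will be again measured 1 minute after standing". Under the words "Potentially clinically significant orthostatic findings include" it names a systolic drop of at least 20 mmHg, a diastolic drop of at least 15 mmHg and a pulse rise of at least 20 bpm. Joined to these by and/or is a fourth item: "Emergence of clinical symptoms (e.g., dizziness) after standing".

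SAP 5.13.4.2 defines orthostatic hypotension by the same three numeric criteria at the same cut-offs, any one of which is enough, "each measured from 5 minutes supine to 1 minute standing at the same visit". Symptoms are not mentioned. The section first plans a count by time period and overall from vital signs, with this rule: "The denominator for percentages is the number of subjects with non-missing data at each visit". It then adds a second, combined figure: "An overall count and percentage of subjects experienced orthostatic hypotension based on findings from either AE records" or vital signs. The AE side of that figure is restricted to the preferred term *Orthostatic hypotension*.

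On the AE profile seen so far, Protocol 1.2 names the commonest classes of event and says: "Central nervous system events included headache, postural dizziness, somnolence (drowsiness), and dizziness". The same section lists orthostatic hypotension separately, among the infrequent events.

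**The concern.** The SAP section is not a pure blood pressure definition: a pulse rise of 20 bpm alone qualifies. It follows the protocol's orthostatic list item by item and stops before the last one, without giving a reason. The combined figure is where clinical events could come back in, but its AE search uses the label that Protocol 1.2 calls infrequent and omits the related symptom that it places among the common events.

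Long-term safety and tolerability is the study's only objective, and Protocol 1.2 also mentions syncopal episodes and injury from falls. The combined figure is the only planned subject-level total that joins AE records with standing measurements, so a reader is likely to take it as the overall orthostatic result. If it omits symptom-only subjects, it understates how many had any orthostatic finding in the protocol's sense.

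**Working it through.** There is no planned figure to reproduce: SAP 2.4 gives no sample size calculation, and neither document gives an orthostatic rate. The check is a comparison of the two sets of rules.

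**Complete readings.** Four findings, each present or absent, give 2^4 − 1 = 15 combinations that are positive under Protocol 6.2.5. The SAP's vital-sign rule needs at least one of the three numeric findings. There are 2^3 − 1 = 7 such sets, each with or without symptoms, so it catches 7 × 2 = 14. The one it misses is symptoms alone. These are patterns, not subjects, so 14 of 15 says nothing about how often the missed one occurs.

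**Standing reading absent.** No numeric criterion can be evaluated. Symptoms are the only protocol finding that can then be met, and the vital-sign rule catches 0 of 1 such patterns.

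**Adding the AE side.** For a subject with symptoms on standing, the combined count works out as follows.

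| Situation | In the combined count? | Visible elsewhere? |
|---|---|---|
| A numeric threshold is met at that or another post-dose visit | Yes | Vital-sign tables |
| No threshold met; AE coded to *Orthostatic hypotension* | Yes | TEAE tables |
| No threshold met; AE coded to postural dizziness or another symptom term | **No** | TEAE tables, under its own term |
| No threshold met; no AE recorded | **No** | No field described |

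The third row is the gap that can be closed with coded data. The documents offer no means of recovering the fourth.

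**Size.** With p the share already counted and s the share of the remainder with only a symptomatic AE, the any-finding total is p + (1 − p)s, and the shortfall is (1 − p)s. Neither p nor s is in the documents. Purely as assumptions, take p from 15% to 40% and s from 3% to 10%:

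- p = 0.15, s = 0.03: 0.15 + 0.85 × 0.03 = 0.176
- p = 0.15, s = 0.10: 0.15 + 0.85 × 0.10 = 0.235
- p = 0.40, s = 0.03: 0.40 + 0.60 × 0.03 = 0.418
- p = 0.40, s = 0.10: 0.40 + 0.60 × 0.10 = 0.460

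The shortfall runs from 1.8 points (0.60 × 0.03) to 8.5 points (0.85 × 0.10). This only restates the assumed s. It shows the form of the effect and is not an estimate for this study.

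**The case against.** The strongest reply is that nothing is hidden. SAP 5.13.1 tabulates every TEAE by system organ class and preferred term, by severity and in descending frequency, and all TEAEs again by time period and age. Recorded postural dizziness or syncope appears there. Protocol 6.2.7.1 asks for a diagnosis rather than a symptom where possible, which steers some cases towards the searched term. A section about hypotension may also reasonably exclude dizziness without any measured change.

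Most of this stands, and it limits the point. It does not remove it. Separate TEAE rows cannot be added to the vital-sign count, because the tables do not show which subjects are in both. The rule on recording diagnoses holds only where possible, and Protocol 1.2 shows that the two kinds of event were reported separately in the programme. The special-interest category in SAP 5.13.1 might cover such terms, but no list is given. Separate rows would keep measured hypotension distinct.

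A reader might also infer three stronger things that the documents do not support:

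- **That symptomatic reactions in general go uncounted.** They do not. Symptomatic subjects who meet a threshold at any post-dose visit, or whose AE carries the one term, are counted.
- **That the most severe cases drop out because they cannot stand for the reading.** This is plausible but is inference. Neither document reports such failures or describes a field for the reason. One qualifying measurement at another visit is enough for the overall count. The non-missing denominator is stated for the vital-sign count; no denominator is given for the combined one.
- **That the SAP made an undeclared deviation.** SAP Section 6 covers departures from the protocol's planned analysis. Protocol 12.1.2 plans summary statistics, percent change and flagged values for vital signs, with no orthostatic incidence. The protocol's list sits in a measurement procedure and calls the findings only potentially significant.

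**Conclusion.** The point holds in a limited form. Followed as written, SAP 5.13.4.2 leaves out of its combined count every subject whose only orthostatic finding is symptomatic, unless the AE happens to be coded to *Orthostatic hypotension*. Against the protocol's list the direction is downward, and this follows from the rules alone. The size cannot be computed: it depends on the rate of symptom-only AEs and on coding practice, neither of which is given. The AE profile in Protocol 1.2 does not supply a rate either, since it spans healthy volunteers and several patient groups at multiple doses up to 160 mg.

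The safety information is incomplete in one composite figure, not missing from the report. This is a worthwhile, low-cost improvement to a descriptive table. It does not call the rest of the safety analysis into question.

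**What to change.** In SAP 5.13.4.2, before the final lock:

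1. Replace the single AE term with a fixed list of preferred terms: *Orthostatic hypotension* plus the terms to which postural dizziness and other symptoms on standing are coded in MedDRA 15.1. A data snapshot has already been taken (SAP 5.12), so choose the list from the terminology and not from observed counts.
2. Show the combined table with separate rows for blood pressure criterion, pulse criterion, AE of orthostatic hypotension and symptomatic AE. Add an any-finding total that counts each subject once.
3. If the eCRF or AE page records that a standing reading was not completed because of symptoms, show those subjects in the symptomatic row. The documents do not show that this is collected, so confirm it first and omit the step if it is not.

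Steps 1 and 2 need only SAP wording and a few table rows built from AEs already coded. The total will be somewhat higher and less favourable, and the symptomatic row may contain some dizziness of other cause. Because the rows are separate, readers can still see measured hypotension by itself.

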#### **5.13.4.3 Weight**

Body mass index (BMI) is calculated from height and weight recorded at each visit. Observed values in weight (kg) and BMI ( $\text{kg}/\text{m}^2$ ) will be summarized with descriptive statistics by time period as defined in [Section 5.4.2 Table 2](#). Within each time period: the highest and lowest measurement from each subject will be summarized. In addition to each time period, the last, highest and lowest measurement collected for each subject during the entire study period will also be summarized.

In addition, a summary table of clinically meaningful weight change will be provided by time period and overall (any timepoint postdose). Two criteria will be applied and tabulated separately: (1) weight increase or decrease  $\geq 7\%$  from baseline; or (2) a BMI  $<19$  or  $>32 \text{ kg}/\text{m}^2$ . Within each time period if a subject has at least 1 measurement meeting the criterion, this subject will be counted as having the incidence for that time period. The denominator for percentages is the number of subjects with non-missing data within each time period.

All observed values for height, weight, and BMI will be provided in a listing with date of collection, study day, and time period. Subjects with a clinically meaningful weight change from baseline will be identified.

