### **5.13.5 Electrocardiogram (ECG)**

#### **5.13.5.1 ECG Parameters and Corrected QT (QTc)**

Observed and change from Baseline values for each time period as defined in [Section 5.4.2 Table 2](#) will be summarized with descriptive statistics for QT, corrected QT (QTcF and QTcB), heart rate, PR Interval, R-R Interval, and QRS Interval. If a subject did not have a baseline ECG assessment, then the last available ECG from the core study will be used as the ACP-103-015 baseline value. For each ECG parameter collected for each subject, within each time period, 2 different representations will be used for generating the population summary statistics: the highest and lowest measurement. The highest or lowest measurement will capture the worst or most extreme observed value. In addition to each time period, for each ECG parameter, the last, highest and lowest measurement collected for each subject during the entire study period will also be summarized. In addition, ECG parameters will also be summarized from pre-PIM baseline and change from pre-PIM baseline. The definition of pre-PIM baseline is: for subjects who received pimavanserin in prior studies, baseline value is obtained from prior-study baseline (pre-exposure); for all other subjects, study -015 baseline is used.

Bazett's corrected QT will be calculated using the formula  $\text{QTcB} = \text{QT} / \sqrt{\text{RR}}$ .

Fridericia's corrected QT will be calculated using the formula  $\text{QTcF} = \text{QT} / \sqrt[3]{\text{RR}}$ .

An additional summary of the proportion of subjects with values of normal or abnormal for each parameter and time period as described above will be provided. Table 3 below lists ECG parameter normal ranges. The proportion of subjects with treatment-emergent abnormally high or abnormally low values will also be presented by time period and overall (at any timepoint postdose).

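### The BMI criterion in the SAP's weight-change table has no baseline condition, so the table cannot separate new from pre-existing out-of-range BMI

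*SAP*

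**What the plan says.** SAP 5.13.4.3 plans the table in these words: "a summary table of clinically meaningful weight change will be provided by time period and overall (any timepoint postdose"). The periods are the safety time periods of SAP Table 2. On the criteria it says: "Two criteria will be applied and tabulated separately". Criterion 1 is a weight change of at least 7% relative to baseline, in either direction. Criterion 2 is a BMI below 19 or above 32 kg/m².

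The counting rule is the same for both: "if a subject has at least 1 measurement meeting the criterion, this subject will be counted as having the incidence for that time period". So is the denominator: "The denominator for percentages is the number of subjects with non-missing data within each time period". Neither rule mentions baseline BMI.

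The analysis set does not supply the missing condition. SAP section 4 uses everyone who received at least one dose, and the eligibility criteria in Protocol 4.1 set no BMI or weight limit.

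**The concern.** Criterion 1 measures change. Criterion 2 measures a level, yet both sit under a heading about change and both are counted as incidence. For criterion 2 the result is a period prevalence that includes everyone who entered the study already outside 19–32.

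This is a single-arm, open-label extension whose only objective is long-term safety and tolerability. With no concurrent control, the subject's own baseline is the main reference for reading a categorical safety table, and criterion 2 does not use it. Because the denominator changes from period to period, the percentage can also rise or fall when out-of-range subjects leave at a different rate from the others, with nobody's weight having changed.

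**Working it through.** **Comparison with the neighbouring safety tables**

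| SAP section | Outcome | How baseline status is handled |
|---|---|---|
| 5.13.3 | Markedly abnormal laboratory values | "tabulated for all subjects and a subset of subjects with normal baseline" |
| 5.13.4.2 | Orthostatic hypotension | "for subjects for whom orthostatic hypotension was not present at baseline" |
| 5.13.5.1 | ECG parameters | "The proportion of subjects with treatment-emergent abnormally high or abnormally low values will also be presented by time period and overall" |
| Appendix B | Hematocrit | Absolute limit combined with a fall of at least 0.03 from baseline |
| 5.13.4.3, criterion 1 | 7% weight change | Defined relative to baseline |
| 5.13.4.3, criterion 2 | BMI below 19 or above 32 | None stated |

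Criterion 2 is the only row without a baseline reference. The data for one exist: SAP 5.9.1 already summarises baseline BMI.

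**Illustration of size**

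The documents give no BMI distribution and no expected rate for this table, so there is no plan figure to reproduce. The inputs are:

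- N = 400, the anticipated minimum enrolment in Protocol 3.4, used only for scale
- b = share out of range at baseline, assumed 5–20%
- s = share of those with an out-of-range value post-baseline, assumed 100%, then 90%
- i = share of subjects in range at baseline who newly cross a limit, assumed 1–5%

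The formulas are:

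- Cases counted under the SAP rule = N·b·s + N·(1 − b)·i
- Percentage shown = cases ÷ N
- Pre-existing share of cases = b·s ÷ [b·s + (1 − b)·i], which does not depend on N

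For b = 10%, i = 3%, s = 100%, the cases are 400 × 0.10 + 360 × 0.03 = 40 + 10.8 = 50.8. That is 50.8 ÷ 400 = 12.7%, and the pre-existing share is 40 ÷ 50.8 = 79%.

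The full grid with s = 100%:

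| b | i | Pre-existing + new | Percentage shown | Pre-existing share |
|---|---|---|---|---|
| 5% | 1% | 20 + 3.8 | 5.95% | 84% |
| 5% | 3% | 20 + 11.4 | 7.85% | 64% |
| 5% | 5% | 20 + 19.0 | 9.75% | 51% |
| 10% | 1% | 40 + 3.6 | 10.9% | 92% |
| 10% | 3% | 40 + 10.8 | 12.7% | 79% |
| 10% | 5% | 40 + 18.0 | 14.5% | 69% |
| 20% | 1% | 80 + 3.2 | 20.8% | 96% |
| 20% | 3% | 80 + 9.6 | 22.4% | 89% |
| 20% | 5% | 80 + 16.0 | 24.0% | 83% |

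With s = 90% the ends of the range barely move: 18 ÷ (18 + 19) = 49% and 72 ÷ (72 + 3.2) = 96%. In the subset with baseline BMI 19–32, the percentage is i itself, 1–5%, against 5.95–24.0% under the SAP rule.

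**The case against.** The strongest reply is that this is one criterion in one descriptive table, and that other outputs show what it hides. SAP 5.13.4.1 summarises change from baseline in weight by period, using each subject's highest and lowest value. SAP 5.13.4.3 summarises highest, lowest and last BMI, tabulates the 7% criterion separately, lists every value and identifies subjects with a meaningful change from baseline. SAP 5.9.1 gives baseline BMI. All of that stands. A reader might infer that shifts in weight or BMI would go unseen in the report. They would not; the limitation belongs to the criterion 2 rows only.

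A reader might also infer that the plan presents these counts as effects of the drug. It does not: 5.13.4.3 makes no attribution, and SAP 5.1 rules out formal tests, so no error rate is involved. Nor does the text establish that gain and loss are merged in one count under criterion 1. It does not specify the rows, and no table shell is in the documents.

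It is fair, too, that the SAP uses incidence loosely for an occurrence within a period, and that absolute categories beside change categories have a precedent in the QTcF summaries of 5.13.5.1. That supports keeping a BMI-level count. It does not support placing it under a weight-change heading with no baseline-normal companion.

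Finally, replacing the count with a restricted one would lose information: further loss in subjects already below 19 would drop out of the row. This point stands, and it argues for adding a subset.

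**Conclusion.** The point holds for criterion 2 of SAP 5.13.4.3. Followed as written, the rule counts subjects already outside BMI 19–32 at baseline as cases in each period in which they remain outside, under a heading about weight change. The table offers no way to tell them from new cases. The consequence is a misleading descriptive percentage; no inference is affected.

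The size is illustrative. With 5–20% out of range at baseline and staying so, and 1–5% new crossings among the rest, about 51–96% of counted cases would be pre-existing. Those inputs are assumptions. If almost no subjects were out of range at baseline, the effect would be small.

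**What to change.** In SAP 5.13.4.3:

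1. Keep the all-subjects count for criterion 2, but label it as BMI out of range post-baseline.
2. Add the count and percentage among subjects with baseline BMI 19–32, applying that condition to both numerator and denominator, as 5.13.3 does with its normal-baseline subset.
3. Show BMI below 19 and BMI above 32 on separate rows in both presentations.
4. State that gain of at least 7% and loss of at least 7% appear on separate rows under criterion 1.

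The cost is a short text change, a few extra rows and a smaller denominator in the subset; no new data are needed. One limit remains. Baseline may be a value from the core study (SAP Definitions), and some subjects received pimavanserin there (SAP 5.11.1). The subset therefore shows what is new since the ACP-103-015 baseline, which for those subjects is not the same as new since starting the drug.

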## APPENDIX B: Criteria for Markedly Abnormal Laboratory Values in SI (Système International) Units

Lab Analyte	Criteria
Chemistry	
Aspartate aminotransferase (AST)	≥ 3 x upper limit of normal
Alanine Aminotransferase (ALT)	≥ 3 x upper limit of normal
Alkaline Phosphatase	≥ 3 x upper limit of normal
Lactate Dehydrogenase (LDH)	≥ 3 x upper limit of normal
Blood Urea Nitrogen (BUN)	≥ 10.71 mmol/L
Creatinine	≥ 176.8 µmol/L
Uric Acid	
Males	≥ 619.5 µmol/L
Females	≥ 501.5 µmol/L
Bilirubin (total)	≥ 34.2 µmol/L
Creatine Kinase (CK)	≥ 3 x upper limit of normal
Hematology	
Hematocrit	
Males	≤ 0.37 and decrease of ≥ 0.03 from Baseline
Females	≤ 0.32 and decrease of ≥ 0.03 from Baseline
Hemoglobin	
Males	≤ 115 g/L
Females	≤ 95 g/L
White Blood Count (WBC)	≤ 2.8 x 10  /L or ≥ 16.0 x 10  /L
Eosinophils	≥ 10%
Neutrophils	Absolute Count < 1.5 x 10  /L
Platelet Count	≤ 100.0 x 10  /L or ≥ 700.0 x 10  /L

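### Incidence rows for weight change, BMI, white cells and platelets combine opposite directions, so they do not show how many subjects crossed each limit

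*SAP*

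**What the plan says.** SAP 5.13.4.3 plans a table of clinically meaningful weight change by time period and overall. "Two criteria will be applied and tabulated separately: (1) weight increase or decrease" of at least 7% from baseline is the first criterion, and BMI below 19 or above 32 kg/m² is the second. The counting rule is: "Within each time period if a subject has at least 1 measurement meeting the criterion, this subject will be counted as having the incidence".

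Appendix B gives one row each to white blood count, "≤ 2.8 x 10 9 /L or ≥ 16.0 x 10 9 /L", and to platelets, "≤ 100.0 x 10 9 /L or ≥ 700.0 x 10 9 /L". These are its only two-sided rows. For the markedly abnormal laboratory tables, SAP 5.13.3 states: "if a subject has at least 1 measurement meeting the marked abnormal criterion, this subject will be counted as having an incidence". This applies per parameter, within each period and for the whole study.

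The SAP also plans outputs that keep direction. For weight and BMI, 5.13.4.3 says "Within each time period: the highest and lowest measurement from each subject will be summarized". For laboratory tests, 5.13.3 summarises "the highest and lowest measurement from that subject during that particular time period". Change from baseline is summarised for weight (5.13.4.1) and for laboratory values (5.13.3).

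**The concern.** Weight loss and weight gain are different safety findings, and so are a low and a high white cell count. SAP 5.13.3 itself recognises that, depending on the test, either extreme or both may be of concern. The protocol makes direction relevant on the blood side. Its background section gives agranulocytosis as a reason for reluctance to use clozapine, section 1.3 names hematologic disorders among the risks to avoid, and section 6.2.2 asks for particular attention to hematological conditions.

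The study is single-arm, with no formal tests (SAP 5.1) and no data safety monitoring board (SAP 5.12). Descriptive counts by period therefore carry much of the safety message, including in the interim analysis for the new drug application. A count that cannot tell the two directions apart is less useful for that purpose. If gains give way to losses from one period to the next, the combined row can stay flat.

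**Working it through.** The plan states no figure to reproduce, so the check is a reading of the criteria and counting rules, followed by an illustration.

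**Reading the rules**

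1. In 5.13.4.3 the word for separate tabulation precedes a list numbered (1) and (2). Increase and decrease both sit inside (1), and both BMI limits sit inside (2). The split is therefore between the two numbered criteria.
2. The counting rule speaks of the criterion and the incidence in the singular. That gives one yes/no outcome per subject, per criterion, per period.
3. Appendix B joins the low and high limits with an or in a single row, and 5.13.3 again refers to one criterion per parameter.
4. No text in 5.13.3, 5.13.4.3 or Appendix B asks for these incidence tables to be split by direction. By contrast, SAP 5.13.5.1 names abnormally high and abnormally low ECG values.

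**Illustration**

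Inputs: N = 400, the anticipated minimum enrolment in Protocol 3.4. All event splits are assumptions, because the documents give no expected rates. N is held fixed for simplicity. The actual denominators are the subjects with data in each period, and these will be smaller later on.

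Formula: subjects in the combined row = n(up) + n(down) − n(both).

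| Assumed gain | Assumed loss | Both | Combined row | Gain row | Loss row |
|---|---|---|---|---|---|
| 40 | 40 | 0 | 80/400 = 20.0% | 10.0% | 10.0% |
| 8 | 72 | 0 | 80/400 = 20.0% | 2.0% | 18.0% |
| 72 | 8 | 0 | 80/400 = 20.0% | 18.0% | 2.0% |
| 50 | 50 | 20 | 80/400 = 20.0% | 12.5% | 12.5% |

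The second and third lines are mirror images with the same printed result. If they described two successive periods, the combined row would show no change. The fourth line shows the effect of counting once: 50 + 50 − 20 = 80.

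For WBC, 10 low with 2 high and 2 low with 10 high both give 12/400 = 3.0%. Counted by direction, they give 2.5% and 0.5%, in opposite order.

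For BMI, the count-once effect is negligible. At fixed height, moving from above 32 to below 19 needs a weight loss of more than (32 − 19)/32 = 40.6%. The loss of direction remains.

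**What the other outputs can recover**

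- Highest and lowest summaries include a minimum and a maximum (SAP 5.1). The minimum of the lowest platelet, WBC or BMI values shows whether anyone reached the low limit, and the maximum of the highest values does the same for the high limit. Neither says how many subjects did.
- Change from baseline for weight is defined as a difference (SAP Definitions), not a percentage. It shows direction, but the 7% limit cannot be read from it exactly.
- Low/normal/high status (5.13.3) covers WBC but not platelets. It uses the laboratory's normal range, not the Appendix B limits.
- Listings hold every value, flag out-of-range laboratory results as low or high, and identify subjects with a clinically meaningful weight change. Counts by direction could be made from them by hand.

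**The case against.** The strongest reply is that direction is not lost from the report. A reader who looks only at the incidence tables might infer that nothing covers weight direction or platelets. That inference is wrong. Highest and lowest summaries exist for weight, BMI and all numeric hematology values, change from baseline is summarised for weight and laboratory tests, and WBC has low/normal/high status. In addition, Protocol 6.2.6.2 asks that the diagnosis behind a clinically significant laboratory abnormality be recorded as an adverse event, and adverse events are tabulated by preferred term. All of this stands.

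A reader might also infer that opposite signals are summed or cancel out. They do neither. The row counts subjects who met either limit, so no affected subject disappears from it. Offsetting arises only when periods are compared, because there is no control arm. The loss of a second event arises only within one period or in the overall column; a subject who meets the criterion in several periods is counted in each.

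Finally, the SAP does not forbid separate rows, and the table shells are not among the documents. Pooling is the natural reading of the singular criterion, not an explicit instruction. That is fair, but it is also a reason to settle the point in the text.

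What remains is narrow: none of the planned summaries gives the number of subjects past the 7%, BMI or markedly abnormal limits in each direction.

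**Conclusion.** The point holds for the incidence rows as written. Four two-sided criteria (weight change, BMI, WBC and platelets) each give one count without direction, and opposite patterns can print the same figure. Weight is the strongest case, because the 7% limit is relative to each subject's baseline and no other planned summary shows it. WBC and platelets are weaker cases, because the minimum and maximum of the extremes show whether a limit was reached; for WBC, normal-range status and the low-only neutrophil row in Appendix B add further cover.

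The size cannot be stated from the documents. The 20.0% and 3.0% figures are illustrations that rest on assumed splits and a fixed N of 400. No threshold, denominator, analysis set or formal inference is affected. This is a free improvement to descriptive reporting, not a flaw that undermines the study.

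**What to change.** In SAP 5.13.4.3, 5.13.3 and Appendix B, state that the following are counted and tabulated as separate rows, by period and overall, at the existing thresholds:

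- weight increase of at least 7% and weight decrease of at least 7%
- BMI below 19 and BMI above 32
- low WBC and high WBC
- low platelets and high platelets

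The combined row may be kept beside them. The cost is a few sentences in the SAP and four extra rows if the combined rows are dropped, or eight if they are kept. No new data are needed.
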